4.4.4 Strength and dosage regimen of the study drugs

Angal S, topical spray [menthol], 0.5 mg + 2 mg/1 ml (Sandoz d.d., Slovenia), the study drug, will be used according to Prescribing Information in the following way: 3 to 5 consecutive presses on the actuator button, 6 to 10 times per day, for 4 days or until full recovery (TSS \leq 2), whichever occurs first during 4 days of therapy. One dose of Angal S is 3 to 5 consecutive presses.

ANTI-ANGIN® FORMULA, topical metered spray, 0.12 mg + 0.24 mg/dose (OOO Valeant, Russia), the comparator drug, will be used according to Prescribing Information in the following way: 1 to 2 consecutive presses on the actuator button, up to 6 times per day, for 5 days or until full recovery (TSS \leq 2), whichever occurs first during 5 days of therapy. One dose of ANTI-ANGIN® FORMULA is 1–2 sprays.

4.5 Expected duration of the subjects' participation in the trial

Screening period: 1 day.

Treatment period: up to 5 days (including the screening/randomization day).

Follow-up period: up to 2 days.

A maximum duration of each subject's participation: 7 days.

A minimum duration of each subject's participation: 6 days (depending on the arm).

4.6 Description of rules for termination of the trial parts or the trial as a whole

The trial may be terminated on the following grounds:

- 1. Upon the Sponsor's initiative: availability of new toxicological or pharmacological data, or data on SAE which require re-consideration of the previous evaluation of the benefit/risk ratio.
- 2. Upon the Sponsor's initiative: AEs incidence or severity require the trial termination;
- 3. Upon the Sponsor's initiative: other reasons including administrative ones.
- 4. Upon the decision of the regulatory authorities.

The trial may be terminated at a specific trial site in case the patients enrollment or data quality are unsatisfactory, or it is reasonable to assume a breach of GCP and/or Declaration of Helsinki, or other serious protocol deviations.

In case of early termination of the trial, the Sponsor must inform the trial site personnel as well as regulatory authorities with indication of the reason thereof.

The rules for trial termination for every participant are described in Section 5.3.

4.7 Record keeping procedures for trial products

The trial sites will be provided with the drugs (the study drug and comparator drug) in the amounts enough for the trial completion, taking into account the planned number of patients to be screened. An authorized trial site specialist shall keep a logbook for the drugs where the drugs receipt to the trial site, dispensing to the subjects, and return of the unused drugs are noted. Storage conditions must be also noted. The study drugs may be used for the purposes of this clinical trial only.

Authorized representatives of the Sponsor or regulatory authorities may check the drugs log or availability of the drugs at stock during the trial site audit/monitoring. The drugs must be stored under the required conditions in a room with an access for the authorized personnel responsible for the drugs dispensing only.

4.8 Storing and unblinding of randomization codes

This is an open trial. The Sponsor will keep a list of the randomization codes. The trial sites will be provided with the sealed envelopes containing randomization numbers. The envelopes must be opened sequentially, from the smaller numbers to bigger ones, to avoid a breach of a randomization principle.

4.9 A list of all the data to be recorded in eCRF

All the data obtained during this clinical trial will be considered to be primary data and subject to record in eCRF.

5 Selection and exclusion of the subjects

5.1 Inclusion criteria

The patients who meet all the inclusion criteria listed below will be included in the trial:

- 1. The Informed Consent Form voluntarily signed by the patient.
- 2. Men and women at the age of 18 to 45 years old, inclusively.
- 3. A diagnosis of acute, uncomplicated, inflammatory and infectious condition of the pharynx associated with the inflammation and pain in the throat.
- 4. Manifestation of the first signs of acute, uncomplicated, inflammatory and infectious condition of the throat (pharyngitis and/or tonsillitis) not more than 48 hours before the inclusion.
- 5. A baseline total sum of TSS (Tonsillopharyngitis Severity Score) points ≥5.
- 6. Body temperature measured in the axillary cavity is less than 37.5 °C.
- 7. Women with childbearing potential should demonstrate a negative pregnancy test result at screening (except for the women after surgical sterilization or menopause for more than 2 years) and use the established contraception methods for at least 3 months before the initiation of the trial therapy and 1 month after completion of the trial.
- 8. Men should use adequate contraception during the trial, since signing of the Informed Consent Form and till the trial completion, and for 30 days after the trial completion.
- 9. Ability to understand the presented information on the clinical trial, readiness to comply with the protocol, ability to use the study drugs by oneself and evaluate the symptoms according to VAS (visual analogue scale) or other questionnaires according to the protocol.

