4.1 General and additional tested parameters

4.1.1 Efficacy parameters

4.1.1.1. The main efficacy endpoint

The primary outcome measure was the percentage of patients without sore throat after 3 days of therapy, on Day 4, as evaluated by the Investigator according to the Tonsillopharyngitis Severity Score (TSS), in both Angal S and ANTI-ANGIN® FORMULA arms.

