4.2.3.2.3 Fill-in of TSS questionnaire

TSS, a questionnaire (point scale) for healthcare professionals, is used in clinical practice as well as in clinical trials to evaluate dynamic changes of symptoms severity of the infection and inflammatory process in the throat (Bereznoy VV, Riley DS, Wassmer G, Heger M. Efficacy of extract of Pelargonium sidoides in children with acute non-group A beta-hemolytic streptococcus tonsillopharyngitis: a randomized, double-blind, placebo-controlled trial). One of such clinical trials with TSS questionnaire was conducted in 2005 in Germany, ©CRO Applertee AG. A version of TSS ©CRO Applertee AG was adapted for this protocol.

TSS (Tonsillopharyngitis Severity Score) is a questionnaire for evaluation of the following symptoms severity: pharyngalgia, difficulty in swallowing, salivation, hyperemia of pharyngeal mucosa, and body temperature increase according to a 4-point scale:

- 0 = no symptom;
- 1 = insignificant symptom;
- 2 = moderate symptom;
- 3 = significant symptom.

The axillary body temperature increase is rated as follows:

- 0 points: <37.5 °C;
- 1 point: 37.5 to <38.5 °C;
- 2 points: 38.5 to <39.5 °C;
- 3 points: >39.5 °C.

TSS is filled in by the Investigator based on the patient complaints and physical examination data. The Investigator summarizes the points obtained for every symptom to obtain a total sum of TSS points. A total sum of TSS points will be used at screening to evaluate for a subject's eligibility and baseline evaluation; on Visit 2 (Day 4), to measure efficacy of the trial therapy in both groups; to evaluate the disease outcomes at Visit 2 (Day 4) and/or Visit 3 (Day 5), where applicable.

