9.2 Planned number of subjects

A statistical objective of the trial will be a prove of a non-inferior therapeutic efficacy and safety of the study drug Angal S comparing to the drug ANTI-ANGIN® FORMULA in the treatment of acute infectious and inflammatory diseases of the pharynx. Justification of a non-inferiority margin is based on the results of a placebo-controlled trial of pastilles with chlorhexidine and lidocaine conducted by [Kris De Ceulaer. A summary of a clinical trial proves that chlorhexidine/lidocaine lozenges are effective and safe. 11-8-2015].

This trial demonstrated absence of a sore throat (a TSS subscale) 3 days after the therapy initiation, on Day 4, in 37.5% patients in the trial arm and 63.1% patients in the placebo arm.

Table 2. Answers distribution results regarding questions on a sore throat at baseline and Day 4

	Baselii	ne visit	Ι)4
N	Product N=106	Placebo N=103	Product N=106	Placebo N=103
Sore throat				
Unknown	0	0	2 (N=104)	0
Absent	0 (0%)	0 (0%)	65 (62.5%)	38 (36.9%)
Mild	3 (2.8%)	3 (2.9%)	27 (26.0%)	45 (43.7%)
Moderate	77 (72.6%)	75 (72.8%)	11 (10.6%)	19 (18.4%)
Severe	26 (24.5%)	25 (24.3%)	1 (1.0%)	1 (1.0%)
p	1.0000		0.0	0016

Therefore, a lower limit of CI boundary may be calculated for the difference in sore throat presence after 3 days of therapy, taking into account 104 participants and 103 patients.

In view of the considered nosology and absence of significant factors requiring a conservative approach for determination of the

non-inferiority margin, for this purpose we can use a two-sided CI 90%. To calculate a two-sided CI 90%, a method described by Newcombe, Robert G. was used "Interval Estimation for the Difference Between Independent Proportions: Comparison of Eleven Methods," Statistics in Medicine, 17, 873-890 (1998). CI 90% will amount to 14.56–36.66%, i.e., the lower limit will correspond to one-sided CI 95%. Therefore, a margin of 14.5% is considered to be justified.

NCSS 8.0 Two Proportions Report

Dataset Untitled

Zero Adjustment Method: None

Note: Exact tests and c.i.'s were not run because total count > 50 (specified under 'Reports' tab).

Table Section

				N1	N2	M1	M2	N
A	В	\mathbf{C}	D	(A+C)	(B+D)	(A+B)	(C+D)	(N1+N2)
65	39	38	65	103	104	104	103	207

Confidence Intervals of Difference (P1-P2)

Interval	Estimated	Confidence	Confidence
Method	Value	Limit	Limit
Chi-Square (Pearson)	0.2561	0.1456	0.3666

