3.4 Subgroups

A subgroup analysis is not envisaged for this trial.

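### The primary analysis ignores the baseline sore-throat score, although entry sets no minimum on that item and the margin comes from a trial with about 97% moderate or severe cases

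*Protocol*

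**What the plan says.** - **Entry (Protocol 5.1).** Criterion 5 is "A baseline total sum of TSS (Tonsillopharyngitis Severity Score) points ≥5". Criterion 3 requires a condition "associated with the inflammation and pain in the throat" but names no level of pain, and no VAS minimum is set. Criterion 6 is "Body temperature measured in the axillary cavity is less than 37.5 °C". Since the TSS scores temperature as "0 points: <37.5 °C" (Protocol 4.2.3.2.3), the fever item is 0 at entry and all five points must come from the other four items.
- **Endpoint (Protocol 4.1.1.1).** "The primary outcome measure was the percentage of patients without sore throat after 3 days of therapy, on Day 4, as evaluated by the Investigator", using the TSS. A patient who starts at "1 = insignificant symptom" and reaches 0 counts the same as one who starts at 3 and reaches 0.
- **Margin (Protocol 9.2).** From one placebo-controlled lozenge trial: "Therefore, a margin of 14.5% is considered to be justified". Table 2 there shows mild sore throat at baseline in 3 of 106 and 3 of 103 patients, none absent, and all others moderate or severe.
- **Analysis (SAP 4.1.2).** A difference in proportions with a 90% Newcombe interval and Fisher's exact test, with no stratification or covariate. Protocol 4.3.1 describes envelope randomization and no stratification factor. SAP 3.4 adds: "A subgroup analysis is not envisaged for this trial". That sentence does not rule out a stratified estimate, but no other part of the SAP plans one.

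**The concern.** A non-inferiority margin taken from an earlier trial protects against a placebo-like drug only if the active-placebo difference in the new trial is about as large as it was in the old one. Sore throat resolves on its own: 36.9% of the placebo patients in the source trial were pain-free on Day 4 although almost all had started moderate or severe. Patients who start with an insignificant sore throat may well be pain-free by Day 4 on any treatment. A large share of them would raise both response rates and narrow the gap between an active and an inactive spray, with no placebo arm to show it. Nothing in the entry rule ties the severity mix to that of the source trial, and nothing in the analysis would show readers how response depended on it.

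A second issue does not depend on the mix. Baseline sore-throat score is probably the strongest available predictor of being pain-free on Day 4. Leaving it out gives up precision and lets a chance imbalance between arms move the estimate.

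**Working it through.** **1. The plan's own figure.** Source trial: 65/104 = 62.5% on product, 38/103 = 36.9% on placebo. (These are the rates in the synopsis and Table 2; the sentence above Table 2 in Protocol 9.2 gives the complements.) Difference 25.6 points. Standard error = √(0.625×0.375/104 + 0.369×0.631/103) = 6.72 points. The 90% interval is 25.61 ± 1.645×6.72 = 14.56 to 36.66, as printed. The margin of 14.5 uses practically the whole lower limit. (The Newcombe method that Protocol 9.2 names gives 14.23 to 36.06; that is a separate matter.)

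**2. Who can enter.** With fever at 0, four items scored 0 to 3 give 190 profiles with a total of at least 5. Criterion 3 in effect rules out the 32 with sore throat 0, leaving 158, of which 44 have sore throat 1 (for example sore throat 1, swallowing 2, hyperemia 2). These are profiles, not patients, and say nothing about how often such patients enrol.

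**3. Possible dilution (assumptions).** The mild share in the source trial was f₀ = 6/209 = 2.9%. Let f be the mild share here and k the drug effect in mild patients as a fraction of that in the others. Then

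effect = 25.6 × [(1−f) + fk] / [(1−f₀) + f₀k],

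and the 14.56 limit scales the same way.

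| Mild share f | k = 0: effect / lower limit | k = 0.5: effect / lower limit | k = 1 |
|---|---|---|---|
| 3% | 25.6 / 14.5 | 25.6 / 14.6 | 25.6 / 14.6 |
| 10% | 23.7 / 13.5 | 24.7 / 14.0 | 25.6 / 14.6 |
| 20% | 21.1 / 12.0 | 23.4 / 13.3 | 25.6 / 14.6 |
| 30% | 18.5 / 10.5 | 22.1 / 12.6 | 25.6 / 14.6 |

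With k = 0, the point effect falls to 14.5 only at 45% mild.

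**4. Chance that a placebo-like drug passes.** Exact enumeration, 128 per arm, 90% Newcombe lower limit above −14.5, k = 0, mild response 75% to 85% in both arms (assumed):

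| Mild share | True source effect 25.6 | True source effect 14.56 |
|---|---|---|
| 3% | 0.03% | 4.9% |
| 20% | 0.3% | 11% |
| 30% | 1% | 16–17% |

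**5. Gain from stratifying.** Let pₘ and pₛ be the response rates in mild and other patients, and p = f·pₘ + (1−f)·pₛ. The share of variance removed is

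1 − [f·pₘ(1−pₘ) + (1−f)·pₛ(1−pₛ)] / [p(1−p)].

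- f = 30%, pₘ = 85%, pₛ = 60%: 1 − 0.2063/0.2194 = 6.0%.
- f = 40%, pₘ = 90%, pₛ = 50%: 1 − 0.1860/0.2244 = 17.1%.
- f = 2.9% (the source mix), same two pairs of rates: 1 − 0.2368/0.2385 = 0.7%, and 1 − 0.2454/0.2499 = 1.8%.

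At the planned 65% and 63% with 128 per arm, the 90% half-width is 1.645 × √[(0.2275 + 0.2331)/128] = 9.9 points. Removing 6% to 17% of the variance shortens it by 3% to 9%, about 0.3 to 0.9 points. Separating moderate from severe could add to this, but the documents give no response rates by those levels.

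**6. Chance imbalance.** A 10-point difference between arms in the mild share moves the unadjusted difference by 0.10 × (85 − 60) = 2.5 to 0.10 × (90 − 50) = 4 points.

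**The case against.** The unadjusted risk difference in a randomized trial is valid, and its interval already allows for chance imbalance. A 10-point imbalance in the mild share is itself only about an 8% to 10% event at 128 per arm with 30% to 40% mild. The assumed mild shares are also far above the only figure in the documents, 2.9%. That all stands. Stratifying is a gain in precision, not the repair of an invalid test, and the gain nearly vanishes at the source trial's mix.

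Much is also planned already. Baseline data are compared between arms (Protocol 9.1.1). SAP Table 18 shows the sore-throat item at each level by arm and visit. The secondary endpoints on TSS symptom reduction and VAS change distinguish a fall from 3 to 0 from a fall from 1 to 0. Readers will therefore see the baseline mix. They will not see Day 4 response within each baseline level, because Table 18 gives only separate distributions at each visit.

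An entry minimum of 2 on the sore-throat item would be slightly stricter than the source population, which included some mild patients. It would also slow enrolment and narrow the population to which the result applies. This stands too, so such a minimum is a trade-off and not a correction.

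**Conclusion.** The mismatch between entry rule, endpoint and margin source is documented, and the primary analysis leaves out the baseline value of its own endpoint. That supports a low-cost improvement to the analysis.

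A reader might go further and infer that the entry rule does dilute the drug effect and so makes a false non-inferiority finding easier. The documents do not support that. They give no expected mild share, no response by baseline severity and no entry criteria for the source trial. Dilution needs both a mild share well above 2.9% and a smaller effect in mild patients; with an equal effect there is none. The error rate of the test against −14.5 points does not change. What is open is whether the margin still stands for a real drug effect in the patients enrolled. If the true source effect is 25.6 points, a placebo-like drug passes about 1% of the time or less up to 30% mild, even with no effect in mild patients. The 11% to 17% figures need three things together: a true effect at the lower confidence limit, no effect in mild patients, and 20% to 30% mild.

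The benefit of stratifying is about 6% to 17% of the variance under assumed response rates with 30% to 40% mild, and 1% to 2% at the source mix.

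**What to change.** In SAP 4.1.2:

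1. Estimate the primary risk difference and its confidence interval stratified by the Visit 1 TSS sore-throat score (≤1, 2, 3), for example a Mantel-Haenszel risk difference or a stratified Newcombe interval. Under 1:1 allocation the Mantel-Haenszel weights are close to the stratum sizes, so the estimate stays on the scale of the 14.5-point margin.
2. Keep the unadjusted difference and its Newcombe interval as a sensitivity analysis.
3. Add a table of Day 4 response by baseline sore-throat score and arm, so that the severity mix and its effect on response can be set against the source trial.

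No new data are needed: the TSS is scored at Visit 1 to establish eligibility, and the ITT definition already requires the Visit 1 procedures. SAP section 1 states that nothing departs from the protocol, so Protocol 9.1.2 needs a matching line, or the change must be recorded as Protocol 9.6 provides. It should be settled before outcome data are examined.

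A minimum sore-throat score at entry, or a short justification that the severity mix will resemble the source trial's, is optional and for the sponsor to weigh.

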5.2 Non-inclusion criteria

The patients who comply with at least one of the criteria listed below will not be included:

- 1. Prior tonsillectomy, tonsillotomy.
- 2. Chronic conditions of the nasopharynx or oropharynx, ulcerative oral disorders.
- 3. History of hypersensitivity or allergic reactions to any components of the study drugs or local anesthetics.
- 4. Use of analgesics during less than 12 hours before the trial start and/or impossibility to discontinue the analgesics for the trial period.

- Protocol No. TE 004 ANG LOZ
 - 5. Use of antibiotics during less than 48 hours before the trial start and/or planned use of antibiotics during the trial.
 - 6. Use of topical drugs (aerosols, gargle solutions. fast-disintegrating tablets/lozenges/pastilles) in the pharynx during less than 12 hours before the trial start and/or impossibility to discontinue topical drugs, except for the study drugs, for the trial period.
 - Use of the systemic, inhalation, or nasal glucocorticosteroids during 30 days before the trial 7. start and/or planned use of the glucocorticosteroids (except for the topical skin drugs) during the trial.
 - Impossibility to discontinue other drugs which might influence the trial results, e.g., 8. antiviral or prohibited concomitant drugs (see *Prohibited concomitant therapy* section), for the trial period.
 - Signs of a primary bacterial pharyngitis or secondary bacterial infection (including body 9. temperature increase above 37.5 °C, purulent pharyngeal pellicles, significant intoxication, leukocytosis, neutrocytosis, WBC differential's shift to the left (increase in stab neutrophils, presence of younger neutrophils), ESR more than 30 mm/h).
 - 10. Granular pharyngitis.
 - Signs of rhinitis, sinusitis, otitis, eustachitis, laryngitis, tracheitis, bronchitis (such 11. conditions require therapy which might influence the trial results).
 - 12. Phenylketonuria.
 - 13. Deficit of saccharase or isomaltase (according to anamnesis data).
 - 14. Glucose-galactose malabsorption (according to anamnesis data).
 - 15. Fructose intolerance.
 - 16. Diabetes mellitus.
 - 17. Glucose-6-phosphate dehydrogenase deficiency (according to anamnesis data).
 - 18. Hemochromatosis.
 - 19. Anemia (Hb less than 120 g/l according to hematology test).
 - 20. Hyperoxaluria.
 - 21. Urolithiasis.
 - Myasthenia. 22.
 - 23. Severe, uncontrolled, cardiovascular condition which, in the Investigator's opinion, preclude the patient from participation in the trial, namely:
 - Severe (IV acc. to Canadian Cardiovascular Society) or unstable angina; a.
 - Decompensated chronic heart failure (NYHA stage IV); b.
 - Myocardial infarction for the last 6 months; c.
 - Uncontrolled arterial hypertension (BP more than 180/115 mm Hg). d.

- 24. Pregnant and/or breastfeeding women.
- 25. Participation in other clinical trials at the screening visit or for 30 days before the screening visit.
- 26. Surgical intervention for 30 days before the screening visit or planned surgical treatment during the trial (before a follow-up visit is completed), including diagnostic procedures or hospital stay.
- 27. Known or suspected narcotic/alcohol abuse.
- 28. A suspected low compliance or incapability of the patient to perform the procedures and comply with restrictions according to the trial protocol (e.g., due to mental disorders).
- 29. Any cardiovascular, renal, hepatic, gastrointestinal, endocrine, or nervous disorders, or any other conditions/diseases which, in the Investigator's opinion, might inflict harm to the patient's health.

5.3 Exclusion criteria

5.3.1 Terms and conditions for the subjects' exclusion from the trial

The subjects may be excluded from the trial on their own free will at any moment, without giving any reason, as well as upon decision of the Investigator or Sponsor in cases when continuation of the participation may inflict harm to the patient's health and/or life. In addition, the patient must be excluded in the cases listed below:

- 1. Negative course of the disease with signs of the secondary bacterial infection (including body temperature increase above 37.5 °C).
- 2. The Ethics Committee, regulatory authorities, or Sponsor terminate the trial or participation of the specific trial site for any reason.
- 3. The Investigator's decision to withdraw the patient from the trial in the interests of the patient.
- 4. Withdrawal of the informed consent (unwillingness of the patient to continue his/her participation in the trial).
- 5. Serious deviation from the trial protocol.
- 6. Individual intolerance of the study drugs.
- 7. Clinically significant adverse event or serious adverse event.
- 8. Patient's non-compliance.
- 9. False inclusion (e.g., the patient was included in breach of the inclusion/non-inclusion criteria).
- 10. The patient complies with the non-inclusion criteria during the trial.
- 11. The patient receives or requires an additional therapy which might influence the trial results or patient's safety (see *Prohibited concomitant therapy* section).

12. Other conditions or events which, in the Investigator's opinion, require the patient's exclusion from the trial.

